Apatinib administration ^[20]			Oral administration once a day after meal						
Apatinib dispensing/retrieval ^[21]			×		×		×		
Imaging Evaluation									
Imaging examination ^[22]	×		Once every 2 cycles in the first 12 cycles of dosing, followed by once every 3 cycles				×		
Follow-Ups After Discontinuation									
Time to progression ^[23]							Imaging evaluations are performed once every 3 months (± 7 d) until disease progression or start of new anti-tumor treatments (for subjects with non-radiological PD)		
Death ^[24]									×
Blood Sampling and Tumor Tissue Sampling									
Blood/tissue sampling for biomarkers ^[26]	×								

Notes:

- [1] Tumor history/past medical history: tumor diagnosis, surgical history, interventional therapy, local ablation therapy, systemic treatment, radiation therapy, as well as past treatments of other conditions, history of cancers other than HCC.
- [2] Concomitant medications and treatments received within 30 days prior to the first dose and during the study period should be recorded. Once a subject discontinues the investigational treatment, only concomitant medication or treatment for new or unresolved treatment-related adverse events are recorded, until 30 days after the last dose.
- [3] Routine blood test: WBC, neutrophils, lymphocytes, RBC, hemoglobin, and platelets. Performed within 7 days prior to enrollment, on Day 15 of Cycle 1, Day 1 and 15 of subsequent cycles, at the end of study, and 30 days after the end of treatment.
- [4] Blood biochemistry: total bilirubin, direct bilirubin, ALT, AST, AKP, γ -GT, total protein, albumin, urea/blood urea nitrogen, creatinine, uric acid, fasting blood glucose, TG, cholesterol, potassium, sodium, chlorine, calcium, phosphorus, blood lipase (only during the screening period and in case of subsequent abdominal pain, abdominal distension and other symptoms of suspected pancreatitis), blood amylase (only during the screening period and subsequent abdominal pain, abdominal distension and other symptoms of suspected pancreatitis). It is carried out within 7 days before enrollment, on Day 15 of Cycle 1, Day 1 and Day 15 of subsequent cycles, at the end of study, and 30 days after the treatment.

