- During the treatment period, the imaging examination should be performed under the same conditions as those of the baseline examination (layer thickness of the scan, use of contrast agent, etc.), and the baseline lesions should be checked every 2 cycles during the first 12 treatment cycles (bone scan will be performed if bone progression is suspected or CR is confirmed), and then once every 3 cycles thereafter. Appropriate examination may also be performed if new lesions are suspected. The first documentation of PR/CR in a subject must be verified 4 weeks \pm 7 days later. A confirmation is required 4-6 weeks after the first documentation of disease progression as per RECIST 1.1 (except those with rapid progression or significant clinical progression);
- The window period for imaging examination schedule is \pm 7 days. Unscheduled imaging examinations can be performed when progressive disease is suspected (such as worsening of symptoms).
- [23] In addition to the progressive disease as evidenced by imaging, subjects who have ended the trial treatment for other reasons must be evaluated at the end of treatment if the imaging examination is not performed within 4 weeks prior to the end of the trial. At the same time, tumor efficacy is followed up every 3 months after the end of the trial until records confirm the progressive disease or initiation of new tumor treatments.
- [24] Survival follow-up: After the trial treatment is discontinued, the survival status and subsequent anti-cancer treatment can be collected through clinical or telephone follow-ups every 1 month until death.
- [25] 10 mL of blood, and paraffin-embedded tumor tissue specimens or fresh biopsy samples (size of a soybean) are collected. At least 10 slides are required, including 3-5 slides of 3-5 μ m thickness for PD-L1, SOAT1, NPC1, and TGF- β testing, and 5-8 paraffin sections (paraffin blocks may be collected directly, without mounting onto slides) of 8-10 μ m thickness, otherwise fresh biopsy samples (pea-size) are required for testing biomarkers such as tumor mutational burden (TMB). See the laboratory manual for blood and tumor tissue sampling/sample collection, and disposal.

Abbreviations

Abbreviations and Terms	Full Name
ADA	Anti-drug antibody
ADRs	Adverse drug reactions
AE	Adverse event
AFP	A-fetoprotein
AKP	Alkaline phosphatase
ALT	Alanine aminotransferase
ANC	Absolute neutrophil count
APTT	Activated partial thromboplastin time
ASCO	American Society of Clinical Oncology

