4.3.2. Procedures for withdrawal or discontinuation

The efficacy and safety examinations to be completed upon trial withdrawal as specified in the protocol must be completed as much as possible. In addition, the safety follow-up should be completed along with fully documented AEs and their outcomes. The investigator can recommend or provide new or alternative treatments to the subject based on the condition of the subject. Patients showing no progressive disease need to be continuously followed-up for imaging evaluation until the subjects begin a new anti-tumor treatment or show progressive disease.

Survival status should still be followed even if the subject refuses to visit the study site, unless the subject withdraws consent to provide further information or consent to be further contacted. In such case, no study assessment is performed, nor any data are collected. The sponsor can retain and continue to use all data collected before withdrawal of informed consent, unless the subject requests a retraction of collected data.

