10. INDEPENDENT IMAGING EVALUATION

On-site imaging review will be performed at each study site, and the Independent Review Committee (IRC) will perform central review on the primary efficacy endpoint of ORR.

Imaging assessments will be performed by an experienced and qualified study physician designated by each study site. All the imaging data related to efficacy assessment should be archived on CD and sent by each study site to the Independent Review Committee for evaluation at regular intervals.

Independent imaging assessment will be performed blindly by two independent radiologists. In the event of disagreement between these 2 independent radiologists, a third radiologist will make the final judgment. See the "Independent Review Committee Charter" for details.

Treatment response will be evaluated by independent radiologists in accordance with the RECIST 1.1 and mRECIST criteria.

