## **4. STUDY ENDPOINTS**

### **4.1. Efficacy Endpoints**

Investigator evaluation is based on RECIST v1.1, and the independent review committee (IRC) is based on RECIST v1.1 and mRECIST to evaluate the following efficacy endpoints: ORR, DCR, TTR, TTP, DOR, and PFS; other efficacy endpoints include OS, 6/9/12/15/18-month survival rates, and TTF. In addition, new anti-cancer treatments mentioned in all efficacy endpoints do not include traditional Chinese medicine anti-cancer treatment with a duration of treatment of 14 days or less.

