**4.1.2.6. Progression-free survival (PFS)**

Progression-free survival (PFS): It is defined as the time from the date of first administration to the date of first recorded tumor progression (assessed as per RECIST v1.1 or mRECIST) or the date of death due to any cause, whichever occurs first.

Censoring rules:

- If there is no baseline tumor measurement or there is baseline tumor evaluation but with missing tumor evaluation after baseline, censoring will be based on the date of first administration.
- If the subject does not have PD or die prior to the termination of the study/cut-off date for analyses or dropout and is not using a new anti-cancer drug prior to PD or death, censoring will be based on the date of the last valid efficacy evaluation.
- If a new anti-cancer treatment has been initiated before PD or death, censoring will be based on the date of the last valid efficacy evaluation prior to the new anti-cancer treatment.

- For death or progression with the absence of two or more planned visits (two visits are planned to be conducted at 26 weeks after 12 cycles of first administration and at 18 weeks prior to 12 cycles), censoring will be based on the date of the last valid efficacy evaluation prior to death or progression.
- For death or PD with the absence of two planned visits after first administration, censoring will be based on the date of first administration.

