### **5.4.4. Subgroup analysis**

In order to evaluate whether the efficacy of this study is consistent among various subgroups, ORR, PFS (evaluated by IRC based on RECIST v1.1), and OS in the following subgroups are analyzed based on FAS. ORR, PFS, OS and 95% CI of each subgroup are estimated, and forest plot of ORR is drawn. The analysis method is the same as those in Sections 5.4.1 and 5.4.2:

- Age (< 65 years, ≥ 65 years)
- Gender (male, female)
- Baseline ECOG PS (0 points, 1 point)
- Extrahepatic metastasis (yes, no)
- Vascular invasion (yes, no)
- Child-Pugh score (5 points, 6 points)
- BCLC stage (stage B, stage C)
- Weight (< 60 kg, ≥ 60 kg)
- HBV infection (yes, no)
- Baseline alpha fetoprotein level (< 400 ng/mL, ≥ 400 ng/mL)
- Baseline alpha fetoprotein level (< 200 ng/mL, ≥ 200 ng/mL)

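### IRC-assessed PFS, TTP and DOR censor patients who stop treatment on a site-called radiological PD that the IRC does not call, which biases these estimates upward, and no planned analysis shows by how much

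*Protocol*

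**What the plan says.** **Imaging after treatment.** In the Protocol's Procedures of the Trial table, the row on time to progression after discontinuation asks for imaging every three months "until disease progression or start of new anti-tumor treatments (for subjects with non-radiological PD". Note [23] exempts subjects who stopped for progression on imaging and runs the follow-up scans "until records confirm the progressive disease or initiation of new tumor treatments". Section 4.3.2 has the same scope: "Patients showing no progressive disease need to be continuously followed-up for imaging evaluation". Section 6.3 agrees.

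**Who calls PD.** Protocol section 10: "On-site imaging review will be performed at each study site". Images are then "sent by each study site to the Independent Review Committee for evaluation at regular intervals". Neither document asks for IRC agreement before treatment or scanning stops.

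**What is scored.** SAP 4.1 has investigators use RECIST 1.1 only, while "the independent review committee (IRC) is based on RECIST v1.1 and mRECIST to evaluate the following efficacy endpoints: ORR, DCR, TTR, TTP, DOR, and PFS". The subgroup analyses in SAP 5.4.4 use "PFS (evaluated by IRC based on RECIST v1.1").

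**Censoring.** Under SAP 4.1.2.4 to 4.1.2.6, a subject with no PD and no new therapy is censored at the last valid efficacy evaluation (for PFS and DOR, also with no death). On new therapy, the PFS rule reads "If a new anti-cancer treatment has been initiated before PD or death, censoring will be based on the date" of the last valid evaluation before that therapy. Death is an event in PFS and DOR, unless it follows new therapy or two or more missed visits. In TTP death is always censored.

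**Scans that do continue.** Protocol 4.3.1 requires a confirmation scan 4-6 weeks after first PD, except in rapid or significant clinical progression. It keeps subjects treated beyond PD on the normal assessment schedule.

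**The concern.** Two readers define progression. The site's call ends treatment and, for those who stop, ends required imaging. The IRC's call makes the event. When the site calls PD and the IRC does not, the subject leaves the IRC risk set on the strength of a site PD call, which itself signals a high risk of early progression. Kaplan-Meier assumes that subjects censored at a given time have the same outlook as those who remain. Here they plausibly do worse, so the IRC curve sits too high.

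TTP is the most exposed, because no later death can count. The mRECIST versions have a further route to disagreement: sites stop on RECIST 1.1, so the stopping PD and the scored PD can differ even with no reader error.

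In an open-label single-arm trial, readers will tend to rely on the IRC versions of PFS and DOR. SAP 5.4.5 plans a table of IRC/investigator agreement, which counts disagreements but does not carry them into the survival estimates.

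**Working it through.** **Plan's own figures.** The documents state no expected PFS, TTP or DOR and no discordance rate. The one related figure that can be checked is the SAP's missed-visit window. Two 8-week intervals plus two 1-week allowances give 2×8 + 2 = 18 weeks, and two 12-week intervals give 2×12 + 2 = 26 weeks. Both match, so I use scans every 8 weeks for 12 cycles and every 12 weeks after that. (Protocol 3.1 and SAP 2.1 state the interval in weeks rather than cycles; the windows fit cycles.)

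**Assumed inputs.** Exponential progression with median m = 5 or 7 months; a share q = 10, 20 or 30% of site PD calls not called by the IRC at that scan; IRC PD one scan later in those subjects; 4.348 weeks per month.

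**Upper bound: no later scan and no deaths.** Twelve months is 52.2 weeks and the seventh scan is at 60 weeks, so 12-month PFS depends on the first six scans.

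- Chance of site PD per 8-week interval: h = 1 − exp(−ln 2 × 8 / (m × 4.348)). For m = 5, h = 0.2251; for m = 7, h = 0.1666.
- IRC PFS had scans continued: (1−h)^6 + q·h·(1−h)^5.
- IRC PFS under the SAP rule, with discordant subjects censored at the site-PD scan: (1 − h(1−q))^6.
- Site PD counted as the event: (1−h)^6, which is 21.6% for m = 5 and 33.5% for m = 7.

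| m | q | Scans continued | SAP rule | Overstated | Site PD as event: low by |
|---|---|---|---|---|---|
| 5 | 10% | 22.3% | 25.7% | 3.4 | 0.6 |
| 5 | 20% | 22.9% | 30.4% | 7.5 | 1.3 |
| 5 | 30% | 23.5% | 35.7% | 12.2 | 1.9 |
| 7 | 10% | 34.2% | 37.7% | 3.6 | 0.7 |
| 7 | 20% | 34.9% | 42.4% | 7.5 | 1.3 |
| 7 | 30% | 35.5% | 47.5% | 12.0 | 2.0 |

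Differences are in percentage points, from unrounded values. A simulation of 200,000 subjects gives the same picture (22.4% against 25.8% in the first row). For scale, the standard error at n = 120 is about √(0.224 × 0.776 / 120) = 3.8 points.

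**Allowing for scans that continue.** Assume 30% of discordant subjects are treated beyond PD and stay on scans, and a share c of the rest are read as IRC PD at the confirmation scan. The share of all site PD calls still censored is q × 0.7 × (1−c): 0.14q at c = 80%, 0.35q at c = 50% and 0.49q at c = 30%. Simulated overstatement of 12-month PFS:

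| c | q = 10% | q = 20% | q = 30% |
|---|---|---|---|
| 80% | 0.5 | 0.9 | 1.4 |
| 50% | 1.2 | 2.4 | 3.6 |
| 30% | about 1.7 (3.4 × 0.49) | 3.5 | 5.4 |

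**Adding deaths.** A separate simulation took PD medians of 4 and 6 months, median survival of 8 months after PD, 50% starting new therapy, and the SAP's 18/26-week windows. For 10, 20 and 30% discordance, 9-month IRC PFS was overstated by about 2, 4-5 and 7 points with no later scan. With 80% having a confirmation scan and 30% treated beyond PD, it was overstated by about 0.5, 1 and 1.5 points.

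**Median.** With no later scan and m = 5 it moves one scan, from 5.5 to 7.4 months, at 10-20% discordance. In the run with deaths it did not move at all. It can only fall on scan dates, so a shift depends on where the curve crosses 50%.

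**The case against.** The strongest reply is that a reader might infer that scanning simply stops at the first site PD, and the Protocol does not say that. Section 4.3.1 requires a confirmation scan and keeps subjects treated beyond PD on schedule; subjects with equivocal, IRC-negative PD could well be among them. Section 7.1.2 adds that tumor assessments are not affected by treatment discontinuation or delay. This stands as a limit on who is affected: only those who stop treatment after site PD. It does not remove the gap, because the specific post-treatment rules still confine imaging to subjects without radiological PD.

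Second, deaths count in PFS and DOR. That offsets part of the bias there, but less so after new therapy or missed visits, and not at all in TTP.

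Third, investigator-assessed PFS already counts site PD as an event. True, but it also changes every other subject's reading. It does not isolate this bias, says nothing about the mRECIST versions, and does not give DOR in IRC responders.

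Fourth, part of the censoring comes from the new-therapy rule and would remain if scans continued. Some IRC-negative calls may also be site over-calls with no progression close behind. Both points stand. Progression soon after censoring is an inference, not something the documents state.

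**Conclusion.** The point holds for subjects who stop treatment on site PD that the IRC does not call. Their censoring in IRC-assessed PFS, TTP and DOR is informative and biases the estimates upward, most for TTP.

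The size cannot be fixed from the documents. At an assumed 10-30% discordance, with 30% treated beyond PD and 30-80% of the rest read as IRC PD at confirmation, 12-month IRC PFS is overstated by about 0.5 to 5 points. That is mostly below the standard error of about 4 points. The figure of about 3.5 to 12 points is an upper bound that needs no later scan at all; it should not be quoted as the expected bias. With no discordance the bias is zero.

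Two stronger readings are not supported. One is that median PFS is inflated by a scan interval; the median may or may not move. The other is that the trial's efficacy conclusion is at risk. The primary endpoint is IRC ORR, the decision rules in SAP section 3 use ORR only, and the sample size rests on ORR. PFS, TTP and DOR are secondary and descriptive. This is a cheap improvement, not a flaw in the main analysis.

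**What to change.** In SAP 4.1.2.4 to 4.1.2.6 and 5.4.2, prespecify a sensitivity analysis of IRC-assessed PFS, TTP and DOR, under RECIST 1.1 and mRECIST. A subject with investigator radiological PD, no IRC PD and no further evaluable scan is counted as an event at the investigator PD date instead of being censored. Show it beside the main IRC estimate, with the number of subjects reclassified.

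The cost is SAP wording and one rerun of the Kaplan-Meier tables on data already collected. No scan, treatment rule or main estimate changes.

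The downside is a less favourable added figure. In the no-later-scan model it errs low by about 0.6 to 2 points at 12 months, and by more if many site calls are over-calls. The two estimates should therefore be read as a bracket. If discordance is negligible they will coincide, which itself shows robustness.

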Study Duration	
Anticipated enrollment of the first subject: March 2018
 
Anticipated enrollment of the last subject: December 2018
 
Anticipated study completion date: December 2019

Procedures of the Trial

Item	Screening Period			Treatment Period (28 days/cycle)			Post-Treatment		Survival Follow-Up
	Within 3 weeks before dosing	Within 1 week before dosing	Cycle 1		Cycles 2–26				Every 1 month (± 3 d)
			Day 1	Day 15	Day 1	Day 15			
				(± 3 d)	(± 3 d)	(± 3 d)	End of Treatment/Withdrawal (+3d)	End of Treatment Visit (± 3 d)	
Baseline Data									
Informed consent	×								
Demographics	×								
Tumor history	×								
Past medical history ^[1]									
Concomitant medication ^[2]	×	×	×						
History of alcoholism	×								
Laboratory Test									
Hematology ^[3]		×		×	×	×	×	×	
Blood biochemistry ^[4]		×		×	×	×	×	×	
Urinalysis ^[5]		×		×	×	×	×	×	
Routine stool test ^[6]		×		×	×		×		
Coagulation function test ^[7]		×		×	×		×		

Compound Code: SHR-1210
Protocol No.: SHR-1210-APTN-II-208-HCC
Final Version 3.0, 29 May, 2019

Item	Screening Period			Treatment Period (28 days/cycle)			Post-Treatment		Survival Follow-Up
	Within 3 weeks before dosing	Within 1 week before dosing	Cycle 1		Cycles 2–26				Every 1 month (± 3 d)
			Day 1	Day 15	Day 1	Day 15	End of Treatment/Withdrawal (+3d)	End of Treatment Visit (± 3 d)	
				(± 3 d)	(± 3 d)	(± 3 d)			
Thyroid function test ^[8]	×				×		×		
Alpha-fetoprotein		×	× (D1 ± 7 d every 2nd cycle)				×		
Examination of hepatitis B and hepatitis C ^[9]	×		× (D1 ± 7 d every 2nd cycle)				×		
Pregnancy test ¹⁰		×					×		
Myocardial zymogram ^[11]		×					×		
Pituitary adrenal axis test ^[12]	×								
HIV test	×								
Clinical Evaluation and Examination									
Adverse event ^[13]	From informed consent to 30 days after the last dose								
Vital signs ^[14]		×	×	×	×	×	×	×	
Physical examination ^[15]		×	×	×	×	×	×	×	
ECOG PS		×			×		×	×	
ECG ^[16]		×		×	×		×		
Echocardiography ^[17]		×					×		

Item	Screening Period			Treatment Period (28 days/cycle)			Post-Treatment		Survival Follow-Up
	Within 3 weeks before dosing	Within 1 week before dosing	Cycle 1		Cycles 2–26		End of Treatment/Withdrawal (+3d)	End of Treatment Visit (± 3 d)	Every 1 month (± 3 d)
			Day 1	Day 15	Day 1	Day 15			
				(± 3 d)	(± 3 d)	(± 3 d)			
Blood pressure monitoring ^[18]	×	×		×	×	×	×		
Investigational Drug									
Administration of SHR-1210 ^[19]			×	×	×	×			

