- [13] Adverse events: Adverse events (AEs) should be recorded from signing the informed consent until at least 30 days after the last dose. SAE and irAE observed within 90 days after the last dose of SHR-1210 should be followed up. If the subjects start a new anti-tumor treatment, they should be followed-up until they start the tumor treatment (if the tumor treatment starts within 30 days after the last dose, the subjects should be followed-up until at least 30 days after the last dose; if the tumor treatment starts over 30 days after the last dose, the subjects should be followed-up until they start the new tumor treatment).
- [14] Vital sign examination: Body temperature, pulse, respiratory rate, and blood pressure. Performed within 7 days before enrollment, on Day 1 and Day 15 of Cycle 1, Day 1 and Day 15 of subsequent cycles, at the end of study, and 30 days after treatment.
- [15] Physical examination: Examination of major body systems (head and face, skin system, lymph nodes, eyes, ears, nose, throat, oral cavity, respiratory system, cardiovascular system, abdomen, urogenital system, musculoskeletal system, nervous system and mental state) is performed within 7 days before enrollment, on Day 1 and Day 15 of Cycle 1, Day 1 and Day 15 of subsequent cycles, at the end of study, and 30 days after the treatment.

Note: Except for baseline examinations, only abnormal findings are documented in the eCRF rather than the entire physical examination (although a comprehensive physical examination is still required).
- [16] 12-Lead ECG: Performed within 7 days before enrollment, on Day 15 of Cycle 1 and Day 1 of subsequent cycles, and at the end of study. Abnormalities in ECG must be confirmed twice via additional ECG tests.
- [17] Echocardiography: performed within 7 days prior to the enrollment and at the end of study, and when clinically significant abnormalities are found during the study.

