6.4. Follow-up

30 days after discontinuation/end of treatment (30 days ± 3 d after the last dose)

[Vital signs] [Physical examination] [ECOG PS] [Routine blood test] [Routine urinalysis]
[Biochemistry] [Adverse events] [Concomitant medication]

Adverse events should be followed-up until at least 30 days after the last dose. SAE and irAE observed within 90 days after the last dose of SHR-1210 should be followed up. If the subjects start a new anti-tumor treatment, they should be followed-up until they start the tumor treatment (if the tumor treatment starts within 30 days after the last dose, the subjects should be followed-up until at least 30 days after the last dose; if the tumor treatment starts over 30 days after the last dose, the subjects should be followed-up until they start the new tumor treatment).

[Survival follow-up] After the trial treatment is discontinued, the survival status and subsequent anti-cancer treatment can be collected through clinical or telephone follow-ups every 1 months until death.

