8. REPORTING OF ADVERSE EVENTS

8.1. Adverse Events (AEs)

8.1.1. Definition of AEs

An AE is any adverse medical occurrence in a study subject, which does not necessarily have a causal relationship with the trial intervention. Adverse events will be collected from the signing of the informed consent form until at least 30 days after the last dose. SAEs and irAEs observed within 90 days after the last dose of SHR-1210 should be followed up and collected. If the subjects start a new anti-tumor treatment, they should be followed-up until they start the tumor treatment (if the tumor treatment is started within 30 days after the last dose, the subjects should be followed-up until at least 30 days after the last dose; if the tumor treatment is started more than 30 days after the last dose, the subjects should be followed-up until they start the new tumor treatment). AEs can include any unfavorable and unexpected symptoms, signs, laboratory abnormalities or diseases, etc., including the following:

- 1) Worsening of pre-existing (prior to enrollment) medical conditions/diseases (including symptoms, signs, and laboratory abnormalities);
- 2) Any new AE: Any new adverse medical conditions (including symptoms, signs, and newly diagnosed diseases);
- 3) Abnormal clinically significant laboratory values or results that are not caused by concomitant diseases.

Any AEs should be recorded in details, including: the name of the AE and description of all relevant symptoms, onset time, severity, causes, correlation with the investigational drug, duration, measures taken, and final results and outcomes.

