8.2.5. Other anti-tumor treatments

SAEs should be recorded from the signing of the informed consent form until 90 days after the last dose of the investigational drug. If the subjects start a new anti-tumor treatment, they should be followed-up until they start the tumor treatment (if the tumor treatment is started within 30 days after the last dose, the subjects should be followed-up until at least 30 days after the last dose of SHR-1210; if the tumor treatment is started more than 30 days after the last dose, the subjects should be followed-up until they start the new tumor treatment). Death that occurs within the SAE reporting period after study treatment is completed should be reported regardless of whether the patient received other treatment.

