- Immune-related TEAE (irAE, including two categories: 1) AE that the investigators determine to be related to SHR-1210 (including definitely related, possibly related, and indeterminable) and corrected with glucocorticoid drugs (except reactive capillary endothelial proliferation); 2) other irAEs that the investigators determine to be related to SHR-1210 without the use of glucocorticoids, with the preferred term for AE provided by medical monitor, see Appendix 3 for details)
- The selected TEAE (the preferred term for AE provided by medical monitor, see Appendix 4 for details)
- The selected TEAE that the investigators determine to be related to SHR-1210 (the preferred term for AE provided by medical monitor, see Appendix 5 for details) and glucocorticoid utilization rate
- No subject with TEAE leading to interruption, dose reduction, and termination of two drugs
- TEAE leading to treatment interruption (apatinib or SHR-1210)
- TEAE leading to treatment termination of two drugs

The incidence of AE is calculated based on the number of subjects having an AE, instead of the number of AE episodes.

AESIs include:

- Grade  $\geq 3$  infusion reaction
- Grade  $\geq 2$  diarrhea/colitis, uveitis, and interstitial pneumonia
- Other Grade  $\geq 3$  irAEs
- Liver enzyme abnormal event: ALT, AST, and total bilirubin (TBIL) are abnormal against baseline
- Grade 4 amylase or lipase increased
- Reactive capillary endothelial proliferation

Among them, the specific definition of liver enzyme abnormal events is as follows:

Baseline Period	Normal (AST/ALT and TBIL)	Abnormal (AST/ALT/TBIL)
Treatment Period	ALT or AST $\geq 3 \times \text{ULN}$ with TBIL $\geq 2 \times \text{ULN}$ and ALP $\leq 2 \times \text{ULN}$ and without hemolysis	AST or ALT $\geq 2 \times \text{baseline level}$ , and $\geq 3 \times \text{ULN}$ or AST or ALT $\geq 8 \times \text{ULN}$ with TBIL increase $\geq 1 \times \text{ULN}$ or TBIL $\geq 3 \times \text{ULN}$

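### SAEs and irAEs are to be collected for 90 days, but the scheduled AE enquiry and the required steroid record reach only day 30; the SAE window also has two different starting points

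*Protocol*

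**What the plan says.** **SAEs and irAEs.** Protocol section 8.1.1 states: "SAEs and irAEs observed within 90 days after the last dose of SHR-1210 should be followed up and collected". Sections 6.1 and 6.4 and schedule note [13] give the same 90 days from the last SHR-1210 dose, but speak only of follow-up. Section 8.2.5, which covers SAEs alone, says: "SAEs should be recorded from the signing of the informed consent form until 90 days after the last dose of the investigational drug".

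**All AEs.** The adverse event row of the schedule reads "From informed consent to 30 days after the last dose". Note [13], attached to that row, makes 30 days a minimum: "Adverse events (AEs) should be recorded from signing the informed consent until at least 30 days after the last dose".

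**Concomitant treatment.** Under note [2], once a subject has stopped treatment, "only concomitant medication or treatment for new or unresolved treatment-related adverse events are recorded, until 30 days after the last dose". Sections 5.5 and 6.1 make the 30 days a minimum.

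**Contacts.** Section 6.4 places the last safety visit 30 days ± 3 days after the last dose. After that, "the survival status and subsequent anti-cancer treatment can be collected through clinical or telephone follow-ups every 1 months until death".

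**irAE definition.** SAP section 5.5.2 has two categories. The first is an "AE that the investigators determine to be related to SHR-1210 (including definitely related, possibly related, and indeterminable) and corrected with glucocorticoid drugs", with reactive capillary endothelial proliferation excepted. The second covers SHR-1210-related events managed without glucocorticoids, through the preferred terms in Appendix 3. That appendix lists endocrine terms only.

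**The concern.** A 90-day window after a PD-1 antibody is there to catch delayed immune toxicity. Here the duty to collect extends to day 90, but the visit, the schedule row and the medication record that would supply the data are set at day 30. In the remaining time, events reach the database only if someone volunteers them.

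The medication record matters because the SAP classifies non-endocrine irAEs by whether a steroid was given. If that fact is not recorded, an event that was correctly reported can still drop out of the irAE count. The loss would carry over to the special-interest category of other Grade 3 or higher irAEs, which must meet the irAE definition. It would also affect the glucocorticoid use rate that the SAP reports for selected SHR-1210-related events.

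A second problem concerns SAEs. Section 5.3 allows either drug to continue alone, so the last SHR-1210 dose and the last dose of any study drug can be far apart. Sites following different sections would then stop collecting SAEs on different dates.

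**Working it through.** The plan gives no figure to reproduce. The check sets the windows side by side and uses day counts.

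| Item | Source | Ends |
|---|---|---|
| All AEs | Schedule row | day 30 after last dose, drug not named |
| All AEs | Note [13], 6.1, 6.4, 8.1.1 | day 30 as a minimum |
| Concomitant treatment | Note [2] | day 30 |
| Concomitant treatment | 5.5, 6.1 | day 30 as a minimum |
| Last safety visit | 6.4 | day 30 ± 3 |
| SAEs and irAEs | Note [13], 6.1, 6.4, 8.1.1 | day 90 after last SHR-1210 dose |
| SAEs only | 8.2.5 | day 90 after last dose of the investigational drug |

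**Step 1: both drugs stop together.** 90 − 30 = 60 days, that is days 31 to 90, lie inside the collection window with no scheduled AE enquiry and no required concomitant steroid record. 60/90 = 67%. Allowing for the visit window, the time without a safety visit is between 90 − 33 = 57 and 90 − 27 = 63 days.

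**Step 2: apatinib continues L days longer.** Assume that the 30-day rules run from the later drug. The gap is then max(0, 90 − (30 + L)) = max(0, 60 − L):

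- L = 0: 60 days
- L = 30: 30 days
- L = 60 or more: 0 days

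New anti-tumor treatment started after day 30 ends follow-up, so it also shortens the window for some subjects. Sixty days is therefore a maximum.

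**Step 3: a late event under the SAP definition.** Both drugs have stopped, an SHR-1210-related pneumonitis starts on day 45, and steroids are given. Section 8.1.1 requires the event to be collected. Category 1 needs evidence of glucocorticoid use, which the medication record is not required to hold after day 30. Category 2 is for events without glucocorticoids and with an Appendix 3 term, and pneumonitis is not listed there. If the steroid is not recorded anywhere, the event meets neither category. The same applies to an onset on day 25 with steroids started on day 35. An endocrine event on the list, managed without steroids, still counts under category 2.

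**Step 4: the SAE anchor.** Counted from the last SHR-1210 dose, the window closes on day 90 under 8.1.1. Under 8.2.5 it closes on day 90 + L, if the investigational drug there means whichever was given last. For L = 60 this is day 90 against day 150. As an example, let SHR-1210 stop at month 6 and apatinib at month 12. The two end dates are then about month 9 and about month 15. An SAE 60 days after the last apatinib dose, at about month 14, falls inside 8.2.5 and outside the 90-day window of 8.1.1.

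In that example the gap in Step 2 is zero, so the two problems fall largely on different subjects.

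**The case against.** The strongest reply is that the plan has a two-tier rule, with all AEs to day 30 and SAEs and irAEs to day 90, abbreviated in one table cell. The adverse event row carries note [13], which sets a minimum and states the 90-day follow-up. A reader might infer that AE recording simply stops at day 30. The documents do not support that, because 8.1.1 expressly requires collection of SAEs and irAEs to day 90. What stands is that a minimum of 30 days requires nothing later, and no scheduled contact is assigned to the remaining days. Section 8.2.7 has the investigator ask about AEs and SAEs at each visit, but does not say that telephone survival contacts count as visits.

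A reader might also infer that irAE incidence will be biased low. That is not shown. AE records (8.1.1) and SAE reports (8.2.6) must state the measures taken, so a steroid may be captured there. The SAP does not say which data define glucocorticoid use, and the documents give no share of irAEs with late onset. Nor would late pneumonitis or hepatitis disappear from the safety report. The SAP's treatment-emergent definition has no end date, the selected-AE lists in Appendices 4 and 5 include pneumonitis, interstitial lung disease and immune-mediated hepatitis without a steroid condition, and section 8.4 of the protocol requires a separate 24-hour report for events of special interest. The exposure is confined to the irAE table and what is derived from it.

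Finally, the anchor conflict might be read as covering irAEs. It does not, because every statement on irAEs is tied to SHR-1210. For SAEs, the general AE window arguably covers the first 30 days after the last apatinib dose, and 8.2.6 keeps later SAEs reportable if drug-related. What depends on the section followed is mainly SAEs judged unrelated on days 31 to 90 after apatinib.

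**Conclusion.** The point holds in a limited form. The 90-day duty in 8.1.1 is not matched by scheduled enquiry or a required steroid record after day 30. The gap is at most 60 of 90 days, when both drugs stop together, and max(0, 60 − L) days if apatinib continues and the last dose means the later drug. A late, steroid-treated, non-endocrine irAE could be missed in the irAE table, in the other Grade 3 or higher irAEs and in the glucocorticoid use rate. This happens only if the steroid is not captured under measures taken or recorded voluntarily. The number of such events cannot be estimated from the documents.

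The SAE anchor conflict between 8.1.1 and 8.2.5 follows from the text and moves the end date by L days when apatinib continues alone, if 8.2.5 refers to the later drug.

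The primary endpoint is not affected. Safety is a secondary objective and the correction is cheap, so it should be made.

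**What to change.** - **Align the windows.** Make the schedule row, notes [2] and [13], and sections 5.5, 6.1 and 6.4 agree with 8.1.1. SAEs and irAEs, and any glucocorticoid or immunosuppressant given for them, are recorded to the end of the 90-day window. Keep the irAE anchor on the last SHR-1210 dose and the existing cut-off at new anti-tumor treatment.
- **State one SAE anchor.** Reconcile 8.1.1 and 8.2.5 to a single date. The later of the two drugs' last doses satisfies both sections, because it contains the shorter window.
- **Use the existing contacts.** Add SAE, irAE and steroid questions to the monthly contacts at about days 60 and 90.
- **Name the data source.** State in SAP section 5.5.2 whether glucocorticoid use is taken from the concomitant medication record, from the measures recorded for the AE, or from both. This is useful even if collection is complete.

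The cost is protocol and SAP wording, small eCRF changes and slightly longer calls. No new visits are needed.
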